### 8.3.1. Period for Reporting Adverse Events

Adverse events and serious adverse events will be collected from the time a patient takes the first dose of Study Treatment in the RVT-901-3004 study until the Follow-up Visit is completed approximately 28 days after the last dose of Study Treatment or the date of initiation of another investigational agent, an alternate therapeutic drug for overactive bladder, or surgical intervention for overactive bladder, whichever occurs first. Events that occurred prior to the patient taking to the first dose of Study Treatment in the RVT-901-3004 study but after the patient provided informed consent to participate in the RVT-901-3003 study will be reported under the RVT-901-3003 study. Serious adverse events reported to the Investigator after the safety reporting period should be reported to the Sponsor if the Investigator assesses the event as related to Study Treatment.

Reporting instructions for serious adverse events are provided in Section 8.3.2.

### 8.3.2. Reporting Serious Adverse Events

All serious adverse events must be **reported in the eCRF within 24 hours of the study site personnel's knowledge of the event**, regardless of the Investigator assessment of the relationship of the event to Study Treatment.

The event term, start date, severity, and initial causality assessment must be entered in the Adverse Event eCRF page and the event must be marked as "Serious". This will activate additional assessment fields including "action taken with study drug", "seriousness criteria", and "brief description" which should be completed as soon as information is available. Marking the event as "serious" will automatically send required notifications for Sponsor review.

The initial serious adverse event report should include:

- The date of the report;
- A description of the serious adverse event (event term, seriousness of the event, date of onset, intensity); and
- Causal relationship to the Study Treatment.

A discharge summary should be provided for all hospitalizations. If the patient died, the report should include the cause of death as the event term (with death as the outcome) and whether the event leading to death was related to Study Treatment, as well as the autopsy findings, if available.

Do not delay reporting a suspected serious adverse event to obtain additional information. Any additional information, if collected, can be reported as a follow-up to the initial report.

All patients who experience a serious adverse event will be evaluated at appropriate time intervals and followed until the event resolves, becomes stable or chronic, or the patient is deemed lost to follow-up. Serious adverse events reported to the Investigator after the safety reporting period should be reported to the Sponsor if the Investigator assesses the event as related to the Study Treatment.

### **8.3.3. Study Treatment Overdose Management**

The medical monitor must be contacted in the event of any Study Treatment overdose.

An overdose is defined as a known deliberate or accidental administration of Study Treatment, to or by a study patient, at a dose above that assigned to that individual patient according to the study protocol.

For this study, any dose of > 2 tablets and/or > 2 capsules of blinded Study Treatment within a 24-hour window is an overdose. There is no known antidote for an overdose.

In the event of an overdose, the Investigator or treating physician should:

- Contact the medical monitor immediately;
- Closely monitor the patient for adverse events and laboratory abnormalities;
- Report all overdose that result in an adverse event within 24 hours of awareness by the study site, using a serious adverse event form according to Section 8.3.2, whether or not the overdose is associated with an adverse event;
- Overdose events that do not result in an adverse event will be reported as a protocol deviation in the eCRF;
- If possible, obtain a plasma sample for pharmacokinetic analysis within 2 days from the date of the last dose of Study Treatment if requested by the medical monitor (determined on a case-by-case basis);
- Document the quantity of the excess dose as well as the duration of the overdosing in the eCRF.

The medical monitor, in consultation with the Investigator, will make decisions regarding patient status and potential dose interruptions, based on the clinical evaluation of the patient.

### **8.4. Assigning Causal Relationship to Study Treatment**

The reasonable possibility of the relationship of an adverse event to Study Treatment is to be assessed with careful medical consideration at the time of evaluation of an adverse event. The following definitions are to be used for the relationship of the adverse event to Study Treatment:

- **Probably related:** A clinical event, including laboratory test abnormality, with a reasonable time sequence to administration of the drug, unlikely attributed to concurrent disease or other drugs or chemicals, or that follows a clinically reasonable response on re-administration (re-challenge) or withdrawal (de-challenge).
- **Possibly related:** A clinical event, including laboratory test abnormality, with a reasonable time sequence to administration of the drug but that could also be

explained by concurrent disease or other drugs or chemicals. Information on drug withdrawal may be lacking or unclear.

- **Not related:** A clinical event, including laboratory test abnormality, with a temporal relationship to drug administration that makes a causal relationship improbable and/or in which other drugs, chemicals, or underlying disease provide a plausible explanation.

All adverse events, whether related to Study Treatment or not, must be fully and completely documented on the adverse event page of the eCRF and in the patient’s clinical record. In the event a patient is withdrawn from the study because of an adverse event, the primary reason for withdrawal (i.e., due to an adverse event) must be recorded on the eCRF as such.

### 8.5. Assigning Severity Rating for Adverse Events

Severity describes the intensity of a specific event (as in mild, moderate, or severe myocardial infarction); the event itself, however, may be of relatively minor medical significance, such as a severe headache. This is not the same as “serious,” which is based on patient/event outcome or action taken.

The Investigator must determine the severity of each adverse event according to the criteria in [Table 5](#).

**Table 5 Criteria for Determining the Grade/Severity of Adverse Event Terms**

Grade	Criteria
1/Mild	Asymptomatic or mild symptoms, clinical or diagnostic observations only; intervention not indicated
2/Moderate	Minimal, local, or noninvasive intervention indicated; limiting age-appropriate instrumental activities of daily living
3/Severe or medically significant	Not immediately life-threatening; hospitalization or prolongation of hospitalization indicated; disabling; limiting self-care activities of daily living
4/Life-threatening	Life threatening consequences; urgent intervention indicated
5/Death	Death related to adverse event

Adverse event severity should be recorded in the appropriate section of the adverse event case report form and in the patient’s source documents.

### 8.6. Adverse Events of Clinical Interest

Selected non-serious and serious adverse events will be reported as Adverse Events of Clinical Interest (AECI) and must be reported **within 24 hours of the study site personnel’s knowledge of the event** as an AECI by marking the appropriate box on the AE eCRF form and assigning the most appropriate category. Additional information requested should be provided as directed in the eCRF Completion Guidelines (eCCGs).

AECIs that also meet the definition of a serious adverse event must be reported as a serious adverse event, as described in Section 8.3.2.

Adverse Events of Clinical Interest for this study include:

- Potential Major Adverse Cardiac and Cerebrovascular Events (MACCE), which will be adjudicated by an independent external expert clinical adjudication committee (CAC) into the following categories according to the definitions in the CAC Charter:
  - Death or any event with fatal outcome
  - Myocardial infarction / Heart Attack
  - Cerebrovascular Accident / Stroke
  - Hospitalization for Unstable Angina / Chest Pain
  - Hospitalization for Heart Failure
  - Coronary revascularization / Angioplasty / Stent
- Hypertension:

An adverse event of hypertension should be reported and will be an AECl as follows:

  - For patients without hypertension (average SBP <140 mmHg, DBP <90 mmHg) at baseline, at two consecutive visits, the average of three systolic blood pressure (SBP)  $\geq$ 140 mmHg or diastolic blood pressure (DBP)  $\geq$ 90 mmHg (or both); at 2 consecutive visits in patients who were not hypertensive at baseline; or,
  - For patients with hypertension at baseline, an increase compared to baseline at 2 consecutive visits in the average of three SBP by  $\geq$ 20 mmHg OR DBP by  $\geq$ 10 mmHg;
  - Initiation of, or increase in dose of, medication for treatment of hypertension in any patient.
- Adverse events consistent with orthostatic hypotension as confirmed by orthostatic vital signs.
- Adverse events suggestive of cystitis or urinary tract infection.
- Elevated AST or ALT lab value requiring that study drug be temporarily withheld or permanently discontinued (see Section 8.6.1 and Section 8.6.2).

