**Physical/ECG/Vitals**

12. A Complete Physical Exam will be performed at the Follow-up Visit.
13. A single 12-lead ECG will be obtained at Week 12.
14. Vital Signs includes Blood Pressure (average of three measurements taken 1-2 minutes apart after sitting for 5 min), Heart Rate, Temperature, Respiration Rate, and Weight.

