## **7. STUDY ASSESSMENTS AND PROCEDURES**

The Schedule of Activities (Section 1.1) summarizes the study assessments/procedures to be performed at each visit. Individual assessments and procedures are described below.

It may be necessary to perform these procedures at unscheduled time points if deemed clinically necessary by the Investigator. Furthermore, additional evaluations/testing may be deemed necessary by the Investigator and/or the Sponsor for reasons related to patient safety. In some cases, such evaluation/testing may be potentially sensitive in nature, and thus local regulations may require that additional informed consent be obtained from the patient. In these cases, such evaluations/testing will be performed in accordance with those regulations.

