### **7.3. Unscheduled Visits**

Unscheduled Visits may be performed at any time during the study whenever necessary to assess for or follow-up on adverse events, at the patient's request, or as deemed necessary by the Investigator. The date and reason for the Unscheduled Visit should be recorded in the source documentation. The specific procedures performed at these visits will be determined by the Investigator, as clinically indicated. The recommended minimum procedures are indicated in the Schedule of Activities (Section 1.1).

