### **7.16. Vital Signs**

Vital signs including blood pressure, heart rate, respiration rate, and temperature (oral or tympanic) will be obtained at all visits after patients have rested quietly in a sitting position for 5 minutes.

Three blood pressure measurements will be taken in a sitting position and performed on the same arm and by the same site staff, if possible, for each patient throughout the study. The following instructions should be followed:

- Sitting systolic and diastolic blood pressures will be determined by averaging 3 replicate measurements obtained 1 to 2 minutes apart. The average of the 3 replicate blood pressure measurements will be used for eligibility and safety assessments (not an individual value).

The same method for assessing temperature should be used at all visits for a particular patient.

Body weight will be measured with patients in street clothing with jacket/coat and shoes removed.

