## **7.17. Adverse Events**

Spontaneously reported adverse events will be recorded at each visit. The Investigator or site staff is responsible for detecting, documenting, and reporting events that meet the definition of an adverse event or serious adverse event. See Section 8 for details on adverse event definitions and reporting.

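### The orthostatic hypotension AECI depends on a confirming measurement that the protocol neither defines nor calls for, so its count will follow site practice

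*Protocol*

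**What the plan says.** Section 8.6 of the protocol names the AECIs. Sites must report them within 24 hours of learning of them, by marking a box on the adverse event form, choosing a category and supplying further information as the eCRF Completion Guidelines direct. One category is "Adverse events consistent with orthostatic hypotension as confirmed by orthostatic vital signs".

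The blood pressure that the protocol specifies is sitting. Section 7.16 states: "Three blood pressure measurements will be taken in a sitting position and performed on the same arm". Table 1 footnote 14 describes it as "Blood Pressure (average of three measurements taken 1-2 minutes apart after sitting for 5 min" and lists no reading in another posture. Section 7.16 adds: "The average of the 3 replicate blood pressure measurements will be used for eligibility and safety assessments (not an individual value".

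On how events come to light, Section 7.17 says: "Spontaneously reported adverse events will be recorded at each visit". On measurements outside the schedule, Section 7 says that "additional evaluations/testing may be deemed necessary by the Investigator and/or the Sponsor for reasons related to patient safety", and Section 7.3 says that "Unscheduled Visits may be performed at any time during the study whenever necessary to assess for or follow-up on adverse events", with the investigator choosing the procedures.

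**The concern.** Confirmation is part of the definition, so an event with no orthostatic reading does not meet the category as worded. The protocol gives no positions, timing, threshold or trigger for that reading. Two sites that see the same complaint can classify it differently, and both would be following the protocol.

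An unconfirmed event loses the AECI flag, the 24-hour AECI report and the additional information that goes with it. The sponsor chose this event for closer attention in a study whose primary objective is long-term safety. A small number in this category would naturally be taken as reassurance, yet it could equally mean that few sites took the reading.

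**Working it through.** **Step 1. Compare the AECI categories in Section 8.6.**

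| Category | What puts an event in it | Does the protocol provide for it? |
|---|---|---|
| MACCE | A potential event, adjudicated afterwards | Yes: adjudication committee and charter |
| Hypertension | Numerical rules on averaged readings at two consecutive visits, or a change in medication | Yes: the scheduled sitting readings and the medication record |
| Liver enzymes | Values that require treatment to be withheld or stopped | Yes: Sections 8.6.1 and 8.6.2, Appendix 4 |
| Cystitis or urinary tract infection | An event suggestive of it; no confirmation needed | Yes: Section 7.18.1 still calls for a dipstick when symptoms are reported |
| Orthostatic hypotension | A consistent event plus confirming orthostatic vital signs | No definition and no trigger |

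In the text at hand, the word orthostatic occurs only in this one item of Section 8.6. The protocol has a symptom-triggered test for urinary infection, where confirmation is not required, and none for orthostatic hypotension, where it is.

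**Step 2. Check the time between visits.** From the study days in Table 1: 113 − 85 = 28; 169 − 113 = 56; 253 − 169 = 84; 308 − 253 = 55; 365 − 308 = 57; 393 − 365 = 28. Up to 84 days separate scheduled visits, so a short-lived episode may be over before the patient is next seen. The documents do not say how often that would happen.

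**Step 3. Illustrate the dependence on site practice.** The protocol states no figure on this point, so there is none to reproduce. Inputs:

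- n = 267 (vibegron) and 233 (tolterodine), the planned arm sizes in the Synopsis.
- p = proportion of patients with an event consistent with orthostatic hypotension. Assumed: 0.5% to 2%.
- q = probability that such an event is confirmed by an orthostatic reading. Assumed: 0 to 1.

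With patients independent and one event each, the expected number with a confirmed event is n × p × q, and the probability of none is (1 − p × q)^n.

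For p = 1%:

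| q | Vibegron: expected | Vibegron: P(none) | Tolterodine: expected | Tolterodine: P(none) |
|---|---|---|---|---|
| 0 | 0 | 1.00 | 0 | 1.00 |
| 0.1 | 267 × 0.001 = 0.27 | 0.77 | 0.23 | 0.79 |
| 0.5 | 267 × 0.005 = 1.33 | 0.26 | 1.17 | 0.31 |
| 1 | 267 × 0.01 = 2.67 | 0.07 | 2.33 | 0.10 |

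Over p = 0.5% to 2%, the vibegron expectation runs from 0.13 to 0.53 at q = 0.1 and from 1.33 to 5.34 at q = 1. For tolterodine the ranges are 0.12 to 0.47 and 1.17 to 4.66.

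At a fixed true rate, the probability of an empty category thus moves from 0.07 to 0.77 as q falls from 1 to 0.1. The protocol does not fix q.

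**The case against.** A reader might infer that the category is empty by construction, with an expected count of zero whatever the true rate. The documents do not support that. The category starts from a reported adverse event, not from routine screening, and the protocol provides for event-driven assessment. Sections 7 and 7.3 allow extra evaluations and unscheduled visits, Table 1 marks vital signs in the unscheduled column, and Section 8.3 requires patients with an adverse event to be evaluated until it resolves or stabilises. Nothing bars a standing reading, and Section 8.6 itself tells the site what kind of measurement confirms. A zero expectation needs q = 0, which the protocol does not imply. This part of the objection stands.

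It is also fair to say that little is lost for the main safety analysis. An unconfirmed event is still documented in full and enters the treatment-emergent incidence by system organ class and preferred term (Sections 9.2.1 and 9.5.2). If serious, it is still reported within 24 hours under Section 8.3.2. The protocol describes no AECI table; that may be in the SAP, which is not at hand. The eCRF Completion Guidelines are not shown either and may say how confirmation is obtained or recorded.

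Finally, asking for objective confirmation is a legitimate choice in favour of specificity, and most other categories in the list rest on some criterion or adjudication. But those criteria are either defined or fed by measurements that the protocol schedules. This one is neither, and permission to take a reading is not an instruction to take it.

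**Conclusion.** The point holds as one of ascertainment. Section 8.6 requires a confirmation that Section 7.16 and Table 1 neither supply nor define. Because the reading is discretionary and unstandardised, the AECI count depends on site practice and is likely to understate the number of events. A low or zero count cannot be taken as evidence that the event did not occur.

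The size cannot be fixed from the documents, since both p and q in the illustration are assumed. What the illustration shows is sensitivity: at 1% incidence among 267 patients, the chance of seeing none ranges from 0.07 to 0.77 for q between 1 and 0.1. The category is near empty only if q is close to 0.

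The consequence is confined to the AECI flag, its 24-hour report and the additional data. The primary endpoint is not affected. The conclusion would soften if the eCRF Completion Guidelines already define the confirming measurement and ask sites to obtain it.

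**What to change.** Reconcile Section 8.6 with Section 7.16 and Table 1 as follows.

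- In Section 8.6, classify every adverse event consistent with orthostatic hypotension as an AECI, whether or not orthostatic vital signs were obtained.
- On the AECI form, add one field for confirmation status: confirmed, not confirmed or not measured.
- Report all such events, with confirmed events as a subset and the number not measured shown beside them.
- The sponsor should state what reading counts as confirming. Without that, the confirmed row would still vary by site, although the not-measured count would make part of that visible.

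This follows the pattern that Section 8.6 already uses for MACCE, where potential events are flagged first and classified afterwards. It needs no new procedure: one line in Section 8.6 and one form field. The cost is some less specific events in the overall row, which the confirmed row separates out, and slightly more 24-hour AECI reports.

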#### **8.6.1. Criteria for Temporary Withholding of Study Treatment in Association with Liver Test Abnormalities**

Elevated liver enzymes or bilirubin sufficient to require withholding study medication must be reported **within 24 hours of the study site personnel's knowledge of the event** using AECl specific CRFs/forms/worksheets provided for the study.

Hepatic enzymes will be monitored in accordance with FDA drug-induced liver injury guidelines [FDA, 2009].

If the following liver test abnormalities develop, Study Treatment should be withheld immediately with appropriate clinical follow-up (including repeat laboratory tests, until a patient's laboratory profile has returned to normal/baseline status), and the event reported as a serious adverse event:

- ALT or AST > 8 x ULN; or
- ALT or AST > 5 x ULN and persists for more than 2 weeks; or
- ALT or AST > 3 x ULN and total bilirubin > 2 x ULN or international normalized ratio (INR) >1.5
- ALT or AST > 3 x ULN with appearance of fatigue, nausea, vomiting, right upper quadrant pain or tenderness, fever, rash and/or eosinophilia (>5%).

Rechallenge may be considered if an alternative cause for the abnormal liver tests (ALT, AST, total bilirubin) is discovered and the laboratory abnormalities resolve to normal or baseline values. The Investigator and Sponsor must discuss and agree with any decision to rechallenge.

Rechallenge should not occur when the etiology of the liver test abnormalities is considered possibly drug induced.

#### **8.6.2. Criteria for Permanent Discontinuation of Study Treatment in Association with Liver Test Abnormalities**

Study treatment should be discontinued permanently if all of the following 4 criteria are met (i.e., potential severe drug-induced liver injury/Hy's law case):

1. Total bilirubin increases to > 2 x ULN or INR > 1.5; AND
2. AST or ALT increases to  $\geq$  3 x ULN; AND
3. Alkaline phosphatase value does not reach 2 x ULN; AND
4. No alternative cause explains the combination of the above laboratory abnormalities; important alternative causes include, but are not limited to the following:
  - Hepatobiliary tract disease;
  - Viral hepatitis (e.g., hepatitis A/B/C/D/E, Epstein-Barr virus);
  - Exposure to hepatotoxic agents/drugs or hepatotoxins, including herbal and dietary supplements, plants, and mushrooms;
  - Alcoholic hepatitis;
  - Non-alcoholic steatohepatitis; or
  - Autoimmune hepatitis.

If an alternative cause for hepatotoxicity is identified, then it should be determined (based on the severity of the hepatotoxicity or event) whether Study Treatment should be withheld or permanently discontinued as appropriate for the safety of the patient.

## **8.7. Pregnancy Management and Reporting to the Sponsor**

If any patient or female partner of a patient becomes pregnant during the study, the site must discontinue the patient from Study Treatment immediately and have the patient return for an Early Withdrawal Visit (Week 52 Visit activities). The Investigator must inform the patient of their right to receive treatment information. If the patient chooses to receive unblinded treatment information, the individual blind should be broken and the treatment assignment provided to the patient. The study team will remain blinded to the patient's treatment assignment.

In the case of a pregnant patient, if she agrees, the Investigator should notify the patient's primary care physician of the pregnancy and provide details of the patient's participation in the study and treatment (blinded or unblinded, as applicable).

In the case of a male patient with a pregnant partner, if the patient agrees, the patient's pregnant partner should be notified and requested to sign a Release of Information form, permitting transfer of information regarding the pregnancy and outcome to the Sponsor.

A pregnancy is to be reported to the Sponsor **within 24 hours of awareness** by the study site personnel, using the pregnancy reporting forms and the contact information in Section 8.3.2. The expected date of delivery or expected date of the end of the pregnancy, last menstruation, estimated conception date, pregnancy result, neonatal data, etc. should be included in this information, as available.

The Investigator will follow the medical status of the mother, the pregnancy, as well as the outcome of the infant at birth, and will report the outcome to the Sponsor.

